7.1 Inclusion Criteria

Subject eligibility is determined according to the following criteria prior to entry into the study:

1. The subject has a diagnosis of type 2 diabetes mellitus.
2. The subject has a fasting C-peptide value of 0.6 ng/mL or higher at the start of the screening period (Week -6) and Week -2 of the screening period.
3. The subject has a hemoglobin value of 10.0 g/dL or higher at the start of the screening period (Week -6) and Week -2 of the screening period.
4. The subject has an HbA1c value of 7.0% or higher but less than 10.0% at Week -2 of the screening period. However, subjects on hemodialysis (patients with end-stage renal failure) with an HbA1c value of less than 7.0% at Week -2 of the screening period are permitted to be enrolled if they have a glycoalbumin value of 20% or higher.
5. <Subjects with a HbA1c value of 7.0% or higher but less than 10.0% at Week -2 of the screening period>

The subject has an HbA1c value difference between the start of the screening period (Week -6) and Week -2 of the screening period within 10.0%* of the HbA1c value at the start of the screening period (Week -6).

<Subjects on hemodialysis (patients with end-stage renal failure) with an HbA1c value of less than 7.0% and glycoalbumin value of 20% or higher at Week -2 of the screening period>

The subject has a glycoalbumin value difference between the start of the screening period (Week -6) and Week -2 of the screening period within 10.0%* of the glycoalbumin value at the start of the screening period (Week -6).

*: rounded to one decimal place

6. The subject has been on a fixed diet and/or exercise therapy (if any) from at least 6 weeks prior to the start of the screening period (Week -6).
7. The subject meets any of the following:
 - The subject has not received any antidiabetic medications (including insulin preparations) from at least 6 weeks prior to the start of the screening period (Week -6).
 - The subject is being treated with 1 oral hypoglycemic drug* starting from at least 6 weeks prior to the start of the screening period (Week -6) at a fixed dose and regimen.

*: Any of the following medications: metformin, acarbose, miglitol, or voglibose

- The subject is being treated with 1 insulin preparation** from at least 6 weeks prior to the start of the screening period (Week -6) at a fixed dose and regimen (≤ 40 units/day).

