3. The criterion was set to require a blood hemoglobin value of 10.0 g/dL or higher in reference to the therapeutic target for renal anemia provided in the “Clinical Practice Guidebook for Diagnosis and Treatment of Chronic Kidney Disease 2012” [7] and “Evidence-based Clinical Practice Guideline for CKD 2013” [8] because a low blood hemoglobin level may affect HbA1c, which is defined as an efficacy endpoint.

4. The criterion was set to define a lower limit of 7.0% because The Evidence-based Practice Guideline for the Treatment for Diabetes in Japan 2013 [9] recommends that the target value of HbA1c should be less than 7.0% from the perspective of prevention of complications. However, since subjects on hemodialysis (patients with end-stage renal failure) may have a low HbA1c level because of factors such as increased immature erythrocytes and shorter erythrocyte lifespan [8], it was decided to take glycoalbumin value additionally into consideration in evaluating subjects with the lower limit of HbA1c level of less than 7.0%. The acceptable glycoalbumin level for such subjects was set at 20% or higher in reference to Best Practice for Diabetic Patients on Hemodialysis 2012 [10]. In addition, the upper limit of HbA1c level was set at 10.0% to exclude subjects with very poor glycemic control with respect to the safety of the subjects.
5. The criterion was set to select subjects with stable glycemic control.
6. The Evidence-based Practice Guideline for the Treatment of Diabetes 2013 [9] recommends to change treatment for patients who cannot achieve the target glucose level despite continuous diet and exercise therapy for 2 to 3 months; therefore, patients who have been on a fixed diet and/or exercise therapy (if any) from at least 6 weeks prior to the start of the screening period (Week -6), i.e., at least 12 weeks prior to the start of Treatment Period I, will be included in this study.

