13.1.3 Efficacy Analysis

(1) Primary endpoint and analytical methods

[Primary endpoint]

Change in HbA1c at the end of Treatment Period I from the end of the screening period (Week 0)

[Primary analysis]

The following analyses will be performed in the FAS.

The population mean change in HbA1c at the end of Treatment Period I from the end of the screening period (Week 0) will be compared between SYR-472 25 mg group and placebo group based on an analysis of covariance (ANCOVA) model for the change in HbA1c at the end of Treatment Period I from the end of the screening period (Week 0) with factors of treatment group and HbA1c at the end of the screening period (Week 0).

The same ANCOVA model will be used to calculate the least square (LS) mean and the two-sided 95% confidence interval (CI) for each treatment group, as well as the intergroup difference in the LS mean between the treatment groups (SYR-472 25 mg group - placebo group) and the two-sided 95% CI.

[Secondary analysis]

For the change in HbA1c at the end of Treatment Period I from the end of the screening period (Week 0), summary statistics (number of subjects, mean, standard deviation, maximum, minimum, and quartiles; hereinafter the same) and two-sided 95% CI for the mean will be calculated for each treatment group, as well as the intergroup difference in the mean between treatment groups (SYR-472 25 mg group - placebo group) and the two-sided 95% CI.

In addition, the same analyses as the primary analysis and the secondary analysis described above will be performed using the PPS to evaluate the robustness of the results in terms of a sensitivity analysis.

[Adjustment for covariates]

The following analyses will be performed in the FAS.

The treatment effect of SYR-472 25 mg will be assessed in consideration of the effects of baseline characteristics based on the ANCOVA model for the change in HbA1c at the end of Treatment Period I from the end of the screening period (Week 0) with factors of treatment group, HbA1c at the end of the screening period (Week 0) and baseline characteristics that may affect the primary endpoint at the blind data review.

(2) Secondary Endpoints and Analysis Methods

[Secondary endpoints]

HbA1c, fasting blood glucose, glycoalbumin

[Analytical methods]

The following analyses will be performed in the FAS.

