2.1 Primary Endpoints and Analysis Methodology

2.1.1 Primary Analysis

Analysis set: Full analysis set

Analysis variables: Change in HbA1c at the end of Treatment Period I from Week 0

Analysis methodology: The population mean change in HbA1c at the end of Treatment Period I from Week 0 will be compared between the SYR-472 25 mg/SYR-472 25 mg group and placebo/SYR-472 25 mg group based on an analysis of covariance (ANCOVA) model for the change in HbA1c at the end of Treatment Period I from Week 0 with factors of treatment group and HbA1c at Week 0. The same ANCOVA model will be used to calculate the least square (LS) mean and the two-sided 95% confidence interval (CI) for each treatment group, as well as the intergroup difference in the LS mean between the treatment groups (SYR-472 25 mg/SYR-472 25 mg group – placebo/SYR-472 25 mg group) and the two-sided 95% CI.

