2.1.2 Secondary Analysis

Analysis set: Full analysis set
Per protocol set

Analysis variables: Change in HbA1c at the end of Treatment Period I from Week 0

Analysis methodology: The analysis (1) will be performed in the “full analysis set” and (2) in the “per protocol set” for the above analysis variables.

- (1) Summary statistics and the two-sided 95% CI for the mean will be calculated for each treatment group, as well as the intergroup difference in the mean between treatment groups (SYR-472 25 mg/SYR-472 25 mg group – placebo/SYR-472 25 mg group) and the two-sided 95% CI.
- (2) In addition, the same analyses as 2.1.1 Primary Analysis and 2.1.2 Secondary Analysis (1) will be performed to evaluate the robustness of the results in terms of a sensitivity analysis.

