2.4.8 Examination of Subgroups

Analysis set:	Full analysis set
Analysis variables:	Change in HbA1c at the end of Treatment Period I from Week 0
Stratum:	
Age (years) [Min≤ - <65, 65≤ - ≤Max]
 
Sex [Male, Female]
 
BMI (kg/m²) (Week 0) [Min≤ - <25.0, 25.0≤ - <30.0, 30.0≤ - ≤Max]
 
Duration of disease (months) [Min≤ - ≤120, 120< - ≤Max]
 
Medication history [Yes, No]
 
Hemodialysis [Yes (end-stage renal failure), No (severe renal impairment)]

	
Use of antidiabetic drugs (Week -6) [Yes, No]
 
Rapid-acting insulin secretagogues [Yes, No]
 
α-glucosidase inhibitors [Yes, No]
 
Insulin preparations [Yes, No]

	
eGFR (mL/min/1.73 m²) (Week 0) [Min≤ - <15, 15≤ - ≤Max]
 
HbA1c (%) (Week 0) [Min≤ - <7.0, 7.0≤ - ≤Max] [Min≤ - <8.0, 8.0≤ - ≤Max]
 
Fasting blood glucose (mg/dL) [Min≤ - <160, 160≤ - =Max] (Week 0)

	
Glycoalbumin (%) (Week 0) [Min≤ - <24, 24≤ - ≤Max]
 
Fasting C-peptide (ng/mL) [Min≤ - <2.0, 2.0≤ - ≤Max] (Week 0)

Analysis methodology:	
The following analyses will be performed for the above analysis variables.
 
(1) Summary statistics and the two-sided 95% CI for the mean will be calculated for each stratum by treatment group, as well as the intergroup difference in the mean between treatment groups (SYR-472 25 mg/SYR-472 25 mg group – placebo/SYR-472 25 mg group) and the two-sided 95% CI.
 
(2) The ANCOVA will be performed for each stratum with the change in HbA1c at the end of Treatment Period I from Week 0 as the response and with treatment group, stratum, and

interactions of treatment group and stratum as factors. The stratum will be included in the ANCOVA model as category variables based on the above category and analyzed.

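### The subgroup ANCOVA in SAP 2.4.8 (2) leaves out Week 0 HbA1c, the covariate of the primary ANCOVA, and so gives up a little precision if baseline and change are correlated

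*SAP*

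**What the plan says.** SAP 2.1.1 compares the arms on change in HbA1c from Week 0 to the end of Treatment Period I, in the full analysis set, by an ANCOVA "with factors of treatment group and HbA1c at Week 0".

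SAP 2.4.8 takes the same response in the same set and lists 16 groupings, counting the two Week 0 HbA1c cut-points separately. It plans two analyses:

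- Analysis (1) is unadjusted: summaries and 95% CIs "will be calculated for each stratum by treatment group", with the difference in means between arms.
- Analysis (2) is called an ANCOVA. Its terms are treatment group, stratum and "interactions of treatment group and stratum as factors". On the form of the stratum it says: "The stratum will be included in the ANCOVA model as category variables based on the above category".

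Baseline-adjusted estimates are planned elsewhere, but only overall:

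- SAP 2.1.2 (2) repeats the primary model in the per protocol set ("the same analyses as 2.1.1 Primary Analysis and 2.1.2 Secondary Analysis (1) will be performed").
- Protocol 13.1.3 describes a further ANCOVA in the full analysis set that adds "baseline characteristics that may affect the primary endpoint at the blind data review".
- SAP 2.4.1, on covariates, only refers back to 2.1.1.

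**The concern.** As written, the model in 2.4.8 (2) has no covariate. It is a two-way analysis of variance with interaction, whatever its label. No other section puts Week 0 HbA1c back into it.

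Only the two Week 0 HbA1c groupings carry baseline directly, each as a two-way split in its own model. Three others can act as proxies at most: fasting glucose, glycoalbumin and hemodialysis. Hemodialysis is linked to baseline because hemodialysis subjects "with an HbA1c value of less than 7.0% at Week -2 of the screening period are permitted to be enrolled" if glycoalbumin is high enough, and because, by the protocol's own account, they "may have a low HbA1c level because of factors such as increased immature erythrocytes".

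If change in HbA1c depends on its starting value within arm and stratum, that variation stays in the residual. The interaction tests, and any stratum-specific treatment differences taken from the model, are then less precise than the collected data allow. Bias is not at stake: adjusted and unadjusted differences estimate the same quantity in a randomised comparison.

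**Working it through.** **Inputs from the documents.** 51 evaluable subjects per arm, so N = 102; SD of change 0.80; assumed difference 0.40 in absolute value; two-sided 5% level (protocol 13.3, SAP section 4).

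**Assumptions, not in the documents.** The correlation r between Week 0 HbA1c and change, within arm and stratum: 0, 0.2, 0.3 and 0.5. Stratum sizes: a 50:50 split, and a stratum holding 30% of subjects.

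**The plan's own figure.** A noncentral-t calculation with 51 per arm, difference 0.40 and SD 0.80 gives 70.56% power, matching the stated 70.6%. It also confirms 86 per arm for 90% power (90.3%). The plan states no figure for the subgroup models.

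**Half-widths without baseline.** A pooled model with a two-level stratum has 102 − 4 = 98 residual df, and t(98) = 1.984.

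- Interaction, 50:50 split (25.5 per cell): 1.984 × 0.80 × √(4/25.5) = 0.629
- Treatment difference in a 30% stratum (15.3 per arm): 1.984 × 0.80 × √(2/15.3) = 0.574
- Treatment difference in a 50% stratum (25.5 per arm): 1.984 × 0.80 × √(2/25.5) = 0.445

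**Half-widths with baseline.** There are 97 residual df, t(97) = 1.985, and the variance is multiplied by (1 − r²)(1 + 1/96). The 1/96 is the expected cost of chance baseline imbalance.

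| 95% CI half-width | Without | r = 0 | r = 0.2 | r = 0.3 | r = 0.5 |
|---|---|---|---|---|---|
| Interaction, 50:50 | 0.629 | 0.632 | 0.619 | 0.603 | 0.547 |
| Difference, 30% stratum | 0.574 | 0.577 | 0.565 | 0.550 | 0.500 |
| Difference, 50% stratum | 0.445 | 0.447 | 0.438 | 0.426 | 0.387 |
| Relative change | – | 0.5% wider | 1.5% narrower | 4.1% narrower | 12.9% narrower |

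**Break-even.** The covariate pays for itself when √(1 − r²) × √(1 + 1/96) × t(97)/t(98) is below 1, that is, when |r| exceeds about 0.10.

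**The two HbA1c groupings.** The split already carries part of baseline. For an assumed median split of a normal baseline it carries 2/π = 63.7% of the variance. The remaining correlation is then 0.122, 0.186 and 0.329 for r = 0.2, 0.3 and 0.5, and the gains fall to 0.2%, 1.2% and 5.1%. The proxy groupings also gain less, to the extent that their categories explain baseline HbA1c.

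**Simulation check.** In 2,000 simulated trials per setting, the half-widths agreed with these formulas to within 0.01.

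**The case against.** The strongest reply is that an unadjusted treatment-by-stratum model is valid in a randomised trial, and that SAP 2.4.5 already treats everything beyond the primary analysis as supportive or exploratory. That is right, and it limits this point to a suggested improvement.

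The benefit also rests on an unknown correlation, and the 12.9% gain belongs to the top of an assumed range. This stands too; certainty attaches to the omission, not to the size of the gain.

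The practical effect is small. Power to detect an interaction as large as the whole assumed effect (0.40) is 24.0% without baseline, 25.6% at r = 0.3 and 30.0% at r = 0.5, with an even split and SD 0.80. With the SDs of 0.523 to 0.628 that protocol 13.3 quotes from the earlier study, the half-width gain at r = 0.3 is only 0.017 to 0.020 percentage points of HbA1c.

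Two points of scope are fair:

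- The SAP takes its stratum differences from analysis (1) and does not say that analysis (2) will report any. The stratum half-widths above compare pooled models without and with baseline. They are not analysis (1)'s intervals, which would be about 0.592 and 0.450 if each used only its own stratum's data.
- The further ANCOVA in protocol 13.1.3 is not carried into SAP 2.4.1, so the protocol is its only source.

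Finally, SAP 2.1.1 does not call Week 0 HbA1c continuous. That reading is inferred from the word ANCOVA and from 2.4.8 having to state separately that strata enter as categories. None of this supplies the missing term.

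**Conclusion.** The concern holds as an inexpensive improvement to consider. SAP 2.4.8 (2) omits the one covariate the sponsor chose for the primary model of the same response in the same set, and no other section restores it by subgroup.

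For groupings unrelated to baseline HbA1c, the cost of the omission is negligible for r near 0.1, about 4% of CI width at r = 0.3 and about 13% at r = 0.5. It is smaller for the HbA1c and proxy groupings. These figures assume 102 evaluable subjects, SD 0.80 and two-level strata; the three-category BMI model differs slightly in degrees of freedom.

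The primary analysis, the sample size and the validity of the subgroup results are unaffected.

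**What to change.** In SAP 2.4.8 (2), for each stratification variable fit one pooled model in the full analysis set with treatment group, stratum category, their interaction and Week 0 HbA1c as a continuous covariate. For the two HbA1c groupings, keep the continuous term beside the category.

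From that model report the adjusted treatment difference with its two-sided 95% CI in each category, and the interaction test (2 degrees of freedom for BMI). Keep analysis (1) as the unadjusted summary that parallels 2.1.2 (1).

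The change is one line of SAP wording before unblinding, minor programming and one degree of freedom per model. No new data and no protocol change are needed. The downside is intervals about 0.5% wider if r is zero. If the sponsor prefers the unadjusted model, the SAP should drop the ANCOVA label and say why baseline is left out.

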2.5 Plasma Concentration of SYR-472Z

Analysis set: Full analysis set

Analysis variables: Plasma concentration of SYR-472Z

Stratum: Hemodialysis [Yes (end-stage renal failure), No (severe renal impairment)]

Visits: Weeks 4 and 12

Analysis methodology: Summary statistics will be calculated for the above analysis variables for each visit in the SYR-472 25 mg/SYR-472 25 mg group among the full analysis set.
The same analysis as the above will be performed for each stratum.

3 SAFETY ANALYSIS

3.1 Treatment-Emergent Adverse Event

3.1.1 Overview of Treatment-Emergent Adverse Events

Analysis set:	Safety analysis set	
Analysis variables:	TEAEs that occur before the start of the study drug for Treatment Period II	
	TEAEs that occur after the start of SYR-472 25 mg tablet	
Categories:	Causality [Related, Not related] Intensity [Mild, Moderate, Severe]	
Analysis methodology:	
The following summaries will be provided for the above analysis variables by treatment group.
 
In the analysis of TEAEs occurring after the start of SYR-472 25 mg tablet, subjects who received SYR-472 25 mg tablet in the safety analysis set will be included in the analyses and the summaries in the consolidated treatment groups will be also provided.
	
	
(1) Overview of TEAEs
 
 1) All TEAEs (number of events, number and percentage of subjects) 2) Causal relationship between all TEAEs and study drug (number of events, number and percentage of subjects) 3) Intensity of all TEAEs (number of events, number and percentage of subjects) 4) TEAEs leading to study drug discontinuation (number of events, number and percentage of subjects) 5) Serious TEAEs (number of events, number and percentage of subjects) 6) Causal relationship between serious TEAEs and study drug (number of events, number and percentage of subjects) 7) Serious TEAEs leading to study drug discontinuation (number of events, number and percentage of subjects) 8) TEAEs leading to death (number of events, number and percentage of subjects) 	
	
TEAEs will be counted according to the rules below:
 
[Number of subjects]
 
 • In the case of “summaries by causality” 
A subject with occurrences of TEAE in both categories (i.e.,
	

“Related” and “Not related”) will be counted once in the “Related” category.

- In the case of “summaries by intensity”

A subject with multiple occurrences of TEAE will be counted once for the TEAE with the maximum intensity.

- In the case of summaries other than the above

A subject with multiple occurrences of TEAE will be counted only once.

[Number of events]

For each summary, the total number of events will be calculated.

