6.0 STUDY DESIGN AND DESCRIPTION

6.1 Study Design

This is a phase 3, multicenter, randomized, double-blind, placebo-controlled, parallel-group, comparative study (Treatment Period I) and a phase 3, multicenter, open-label, long-term study (Treatment Period II) using placebo as a control to evaluate the efficacy and safety of SYR-472 when administered orally at a dose of 25 mg once weekly in patients with type 2 diabetes mellitus complicated by severe renal impairment or end-stage renal failure and with inadequate glycemic control despite diet and/or exercise therapy (if any) or despite treatment with 1 antidiabetic drug (Table 6.a) in addition to diet and/or exercise therapy (if any).

Table 6.a Concomitant Antidiabetic Drugs Permitted in the Study

Type	Drug Name (Nonproprietary Name or Class)
Rapid-acting insulin secretagogues	Mitiglinide calcium hydrate, repaglinide
α -glucosidase inhibitors	Acarbose, miglitol, voglibose
Insulin preparations	Mixed, intermediate-acting, or long-acting soluble insulin (40 units/day or less*)

*: For change in the dosing unit of insulin preparations, see 2 (2) in Section 7.3.

[figure not shown]
Subjects who enter the screening period after signing informed consent and are considered eligible according to the inclusion and exclusion criteria will be randomly assigned to either of the SYR-472 25 mg group or placebo group. Subjects who are assigned to the SYR-472 25 mg group in Treatment Period I will continue to be treated with SYR-472 25 mg in Treatment Period II, while those assigned to the placebo group will be switched to SYR-472 25 mg in Treatment Period II.

In Treatment Period I, 1 SYR-472 25 mg tablet or placebo tablet will be orally administered once weekly before breakfast. In Treatment Period II, 1 SYR-472 25 mg tablet will be orally administered once weekly before breakfast.

The study period consists of 6 weeks of screening, 52 weeks of treatment, and 2 weeks of follow-up, a total of 60 weeks. The treatment period consists of Treatment Period I (double-blind) between Week 0 and Week 12 and Treatment Period II (open-label) between Week 12 and Week 52. Subjects will visit the site at the start of the screening period (Week -6), Week -2 of the screening period, end of the screening period (Week 0), Week 2 and Week 4 of the treatment period, and at every 4 weeks until Week 52 of the treatment period, and at the end of the follow-up period (Week 54) (total of 18 visits).

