10.2 Procedures

10.2.1 Collection and Reporting of AEs

10.2.1.1 PTE and AE Collection Period

Collection of PTEs will commence from the time the subject signs the informed consent to participate in the study and continue until the subject is first administered study drug (Visit 3). For subjects who discontinue prior to study drug administration, PTEs are collected until the subject discontinues study participation.

Collection of AEs will commence from the time that the subject is first administered study drug (Visit 3). Routine collection of AEs will continue until Visit 18.

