- Study Day: The day before the start of the study drug administration will be defined as Day -1 and the day of the start of the study drug administration will be defined as Day 1.
- Follow-up Day for Treatment Period I: The day after the last administration of the study drug for Treatment Period I will be defined as Follow-up Day 1 for Treatment Period I.
- Study Day for Treatment Period II: The day before the start of the study drug administration for Treatment Period II will be defined as Day -1 for Treatment Period II and the day of the start of the study drug administration for Treatment Period II will be defined as Day 1 for Treatment Period II.
- Study Day for SYR-472 25 mg tablet: The day before the start of SYR-472 25 mg tablet will be defined as Day -1 for SYR-472 25 mg tablet and the day of the start of SYR-472 25 mg tablet will be defined as Day 1 for SYR-472 25 mg tablet.
- Follow-up Day for SYR-472 25 mg tablet: The day after the last administration of SYR-472 25 mg tablet will be defined as Follow-up Day 1 for SYR-472 25 mg tablet.
- Treatment groups: SYR-472 25 mg group (subjects who received SYR-472 25 mg in both Treatment Periods I and II), placebo group (subjects who received placebo in Treatment Period I and SYR-472 25 mg in Treatment Period II).

In this statistical analysis plan (hereinafter referred to as SAP), the treatment groups will be presented as the SYR-472 25 mg/SYR-472 25 mg group and the placebo/SYR-472 25 mg group.

- Summary statistics: number of subjects, mean, standard deviation, maximum, minimum, and quartiles
- Reason for not being treated with the study drug for Treatment Period II: If the subject is “Not treated” with the study drug for Treatment Period II, the reason why the administration of study drug was discontinued will be analyzed as the reason for not being treated with the study drug for Treatment Period II.
- Treatment-emergent adverse event (TEAE): An adverse event whose date of onset occurs on or after the start of the study drug administration. Since there is a possibility that the evaluation result of an adverse event may differ before and after the start of the study drug administration for Treatment Period II, the evaluation result of adverse event to be used for analysis will be defined according to the rules below:

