3.1.2 Displays of Treatment-Emergent Adverse Events

Analysis set:	Safety analysis set	
Analysis variables:	TEAEs that occur before the start of the study drug for Treatment Period II	
	TEAEs that occur after the start of SYR-472 25 mg tablet	
Categories:	Intensity	[Mild, Moderate, Severe]
	Time of onset (day)	TEAEs that occur before the start of the study drug for Treatment Period II
		[1-28, 29-56, 57-Max]
		[1-14, 15-28, 29-Max]
		TEAEs that occur after the start of SYR-472 25 mg tablet
		[1-84, 85-168, 169-252, 253-336, 337-Max]
		[1-14, 15-28, 29-Max]
	Number of days from the immediate study drug administration (days)	[1, 2, 3, 4, 5, 6, 7, 8-Max]
Analysis methodology:	
The following summaries will be provided for the above analysis variables using frequency distributions by treatment group.
 
In the analysis of TEAEs occurring after the start of SYR-472 25 mg tablet, subjects who received SYR-472 25 mg tablet in the safety analysis set will be included in the analyses and the summaries in the consolidated treatment groups will be also provided concerning (1) and (4).
	

TEAEs will be coded using MedDRA dictionary and will be summarized based on SOC and PT. SOC will be sorted alphabetically and PT will be sorted in decreasing frequency for tables provided by SOC and PT. SOC and PT will be sorted in decreasing frequency for tables provided by SOC only or PT only.

- (1) All TEAEs by SOC and PT
- (2) All TEAEs by SOC
- (3) All TEAEs by PT
- (4) Drug-related TEAEs by SOC and PT
- (5) Intensity of all TEAEs by SOC and PT
- (6) Intensity of drug-related TEAEs by SOC and PT
- (7) TEAEs leading to study drug discontinuation by SOC and PT
- (8) Serious TEAEs by SOC and PT
- (9) All TEAEs by SOC and PT over time
- (10) Number of days from the immediate study drug administration for all TEAEs by SOC and PT
- (11) TEAEs whose incidence summarized by PT is 2% or higher (rounded off to the first decimal place) in either treatment group by SOC and PT
- (12) Intestinal obstruction-related TEAEs by SOC and PT
- (13) Acute pancreatitis-related TEAEs by SOC and PT
- (14) QT/QTc interval prolongation-related TEAEs by SOC and PT
- (15) Hypersensitivity-related TEAEs by SOC and PT
- (16) Cardiovascular TEAEs by SOC and PT
- (17) Pemphigoid TEAEs by SOC and PT
- (18) Renal impairment TEAEs by SOC and PT
- (19) Hypoglycemia-related TEAEs by SOC and PT

The frequency distribution and incidence will be provided according to the rules below:

[Number of subjects]

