3.3 Clinical Laboratory Evaluations and Other Safety Endpoints

3.3.1 Clinical Laboratory Evaluations

3.3.1.1 Hematology and Serum Chemistry

Analysis set:	Safety analysis set		
Analysis variables:	Hematology		
	Red blood cells	Reticulocytes	White blood cells
	Hemoglobin	Hematocrit	Platelets
	Neutrophils	Lymphocytes	Monocytes
	Eosinophils	Basophils	MCV
	MCH	MCHC	
	Serum chemistry		
	ALT	AST	
	γ-GTP	ALP	
	Total bilirubin	Total protein	
	Albumin	Creatinine	
	Amylase	Lipase	
	Blood urea nitrogen	Uric acid	
	Creatine kinase	LDH	
	Total cholesterol	Triglyceride	
	LDL cholesterol	HDL cholesterol	
	High-sensitivity CRP	K	
	Na	Ca	
	Cl	P	
	Fe	Creatinine clearance	
Categories:	Adjudication results based on the normal reference ranges [Low, Normal, High]		
Visits:	Weeks -6, -2, 0, 2, 4, 8, 12, 16, 20, 24, 28, 32, 36, 40, 44, 48, 52, and		

Analysis methodology: The following analysis will be performed for the above analysis variables except for high-sensitivity CRP and creatinine clearance by treatment group. The following analyses of (1) to (2) will be performed for high-sensitivity CRP and creatinine clearance by treatment group.

When the analysis of MAV is performed, if both “upper” and “lower” criteria in the MAV Criteria are applicable to the same test item, the analysis will be performed for each criterion separately. See Appendix 2 of this SAP for the definitions of test items subject to this analysis and the MAV Criteria.

- (1) Summary statistics for each visit and summary statistics for change from Week 0 at each visit after Treatment Period I
- (2) Case plots
- (3) Shift tables showing adjudication results based on normal reference range at Week 0 and each visit after Treatment Period I
- (4) Frequency distributions for MAV before the start of the study drug administration for Treatment Period II and after the start of SYR-472 25 mg tablet

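### The by-group tables of TEAEs and markedly abnormal values after the first SYR-472 tablet set about 54 weeks of observation beside about 42, and most give nothing that allows for the difference

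*SAP*

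**What the plan says.** Under Protocol 6.1, subjects randomized to SYR-472 take it from Week 0, while "those assigned to the placebo group will be switched to SYR-472 25 mg in Treatment Period II", at Week 12. The SAP definitions keep this as the grouping for every table, with the "placebo group (subjects who received placebo in Treatment Period I and SYR-472 25 mg in Treatment Period II") shown as placebo/SYR-472. Protocol 10.2.1.1 states "Routine collection of AEs will continue until Visit 18", for both groups alike.

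One of the two TEAE analysis variables is "TEAEs that occur after the start of SYR-472 25 mg tablet", with the day of the first such tablet as day 1. For it, SAP 3.1.1 says "The following summaries will be provided for the above analysis variables by treatment group", and adds the consolidated groups. The entries are of the form "All TEAEs (number of events, number and percentage of subjects").

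SAP 3.1.2 counts subjects only. Apart from the over-time display, its percentages are taken over the subjects in the analysis set. Consolidated columns are given only for items (1) and (4), which are all TEAEs and drug-related TEAEs by SOC and PT.

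For laboratory tests, SAP 3.3.1.1(4) plans "Frequency distributions for MAV before the start of the study drug administration for Treatment Period II" and likewise after the start of SYR-472, by group. SAP 3.3.2.2(3) does the same for ECGs.

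Two items bear on observation time. Item 3.1.2(9) shows all TEAEs by SOC and PT in time intervals, with subjects at risk as the denominator. SAP 1.3.1 tabulates the number of SYR-472 administrations and the duration of SYR-472 exposure by group.

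**The concern.** The clock starts at the first SYR-472 tablet in each group but stops at the same study visit, so the placebo/SYR-472 group is observed for about 12 weeks less. A percentage of subjects with at least one event rises with observation time, and so does a count of events. Two columns over unequal periods therefore differ in expectation even when the drug behaves identically in both groups. The same holds for MAVs, where the group tested more often has more chances to cross a limit. A consolidated percentage averages the two observation lengths.

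Adverse events are the primary safety endpoint and long-term safety is a stated objective (Protocol 5.1 and 5.2.1). These tables are its main output. Read side by side, they could suggest that risk accumulates with longer treatment when it does not, or hide a hazard that falls over time.

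**Working it through.** **Schedule.** Protocol 6.1 states 18 visits. Counting them: Weeks -6, -2 and 0 (3), Weeks 2 and 4 (2), Weeks 8 to 52 every 4 weeks (12), and Week 54 (1); 3 + 2 + 12 + 1 = 18. Visit 18 is therefore Week 54, as stated.

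**Observation after the first SYR-472 tablet.**
- SYR-472/SYR-472: 54 - 0 = 54 weeks (378 days).
- placebo/SYR-472: 54 - 12 = 42 weeks (294 days).
- Ratio 54/42 = 1.29. The treatment periods alone are 52 and 40 weeks, ratio 1.30.

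**Subjects with an event.** Assume the same constant hazard in both groups and full follow-up. If p is the proportion at 42 weeks, the proportion at 54 weeks is 1 - (1 - p)^(54/42).

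| placebo/SYR-472 (42 weeks) | SYR-472/SYR-472 (54 weeks) |
|---|---|
| 5% | 6.4% |
| 20% | 24.9% |
| 40% | 48.1% |
| 60% | 69.2% |
| 90% | 94.8% |

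The gap is largest in the middle of the range, about 9 points (50% becomes 59.0%).

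**Event counts.** The expected ratio is 1.29 when the true rate ratio is 1.00. With 53 per group and an assumed 1 event per subject-year, 53 × 54/52 = 55 against 53 × 42/52 = 43. At 4 per subject-year it is 220 against 171.

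**Tests that can yield a MAV**, from the SAP visit lists. The Week 12 assessments precede the first SYR-472 tablet in the placebo/SYR-472 group.
- Laboratory: Weeks 2, 4, 8, ..., 52 and 54 = 15, against Weeks 16, 20, ..., 52 and 54 = 11.
- ECG: Weeks 4, 12, 24, 36, 52 and 54 = 6, against Weeks 24, 36, 52 and 54 = 4.
- With an assumed independent chance q per laboratory visit, the proportions of subjects with any MAV are 1 - (1 - q)^15 and 1 - (1 - q)^11. For q = 1%, 2% and 5% these are 14.0% against 10.5%, 26.1% against 19.9%, and 53.7% against 43.1%.

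**How far 3.1.2(9) helps.** Its main intervals are days 1-84, 85-168, 169-252, 253-336 and 337-Max from the first SYR-472 tablet. The first three are fully observed in both groups. In 253-336 the placebo/SYR-472 group is observed for 294 - 252 = 42 of 84 days, yet a subject with any exposure or TEAE during or after the interval counts in full. In 337-Max that group has practically no planned observation. So the display is comparable to day 252, and it covers all TEAEs only.

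**Would a 40-week window settle the MAV comparison?** To SYR-472 day 281, laboratory visits fall on days 15, 29, 57, ..., 281 (11) against 29, 57, ..., 281 (10). ECGs fall on days 29, 85, 169 and 253 (4) against 85, 169 and 281 (3). Testing stays unequal.

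**The case against.** The strongest reply is that nothing inferential rests on these columns. No test, difference or confidence interval is planned for TEAEs. The randomized safety comparison is the separate table of TEAEs before Treatment Period II, where planned follow-up is equal. The group labels show the design, SAP 1.3.1 reports the unequal exposure, and the post-SYR-472 subgroup tables in 3.1.3 use consolidated groups only. All of this stands, and it limits the point to how descriptive tables are read. It does not remove the point, because the exposure table is not linked to the event tables and the main ones are still laid out by group.

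Four stronger readings are tempting, and the documents do not support them.
- A reader might infer that no denominator allows for time. Item 3.1.2(9) does so by interval, and lists every PT. What it lacks is serious, drug-related, discontinuation and grouped special-interest results, and MAVs.
- A reader might infer that the SYR-472/SYR-472 column is bound to be higher. With 53 per group, the gaps for 20%, 40% and 60% are about 0.6, 0.8 and 1.0 standard errors, so that column would be higher in roughly 73%, 80% and 84% of trials.
- A reader might infer that event counts are planned throughout. They are specified in 3.1.1, but not in 3.1.2 or for MAVs.
- A reader might infer that the consolidated percentage has no defined period. The period is defined, from the first SYR-472 tablet to Visit 18; only its length varies.

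It is also fair to object that subject-year rates assume a constant hazard. If events cluster early, the group observed for less time would look worse on a rate.

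**Conclusion.** The point holds as one about presentation. The post-SYR-472 TEAE and MAV tables compare groups with planned observation in a ratio of about 1.29, and with 15 against 11 laboratory visits and 6 against 4 ECGs. Under equal constant hazards and full follow-up, the expected gap in subjects with an event is about 5 points at 20% and 8 to 9 points in mid-range. These sizes are illustrations. Withdrawals would change the observation times, and the placebo/SYR-472 column contains only subjects who went on to receive SYR-472, a selection that the arithmetic ignores. The MAV criteria are in SAP Appendix 2, which is not in the available text, so the MAV part rests on the section wording and the visit schedule. The controlled comparison in Treatment Period I is not touched. This is a cheap improvement to the long-term safety tables and does not correct any planned inference.

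**What to change.** For the post-SYR-472 analyses in SAP 3.1.1 and 3.1.2 of all, drug-related, serious, discontinuation and special-interest TEAEs, add by group and consolidated:
- subjects with an event, and events, per 100 subject-years of observation from the first SYR-472 dose;
- the percentage of subjects with an event within the common window of 42 weeks (294 days) after the first SYR-472 dose, which does not rely on a constant hazard.

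For MAVs in 3.3.1.1 and 3.3.2.2, show by group the number of tests performed after the first SYR-472 dose and the proportion of tests meeting the criterion, next to the subject frequency. A 40-week window alone would not equalise testing.

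The existing crude tables can stay. The cost is SAP wording and longer tables. The dates are already collected, and the SAP already derives duration of exposure from the first and last SYR-472 administrations.
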